#### 5.5.9 Faeces sampling

Sampling will be performed using stool collection tubes by Sarstedt, Nümbrecht, Germany, using a stool collector (Süsse Stuhlfänger, Gudensberg, Germany). Directions for safe and hygienic fecal collection will be delivered to the probands in words as well as in pictograms. Bacterial DNA will be extracted from stool samples using the MagNA Pure LC DNA Isolation Kit III (Roche). The 16S rRNA gene will be amplified in a PCR reaction and sequenced with next-generation sequencing technology (Roche Genome Sequencer FLX or Illumina MiSeq) and interpreted by the respective software analyzers.

#### 5.6 Benefit-Risk Assessment

Empagliflozin has been studied in subjects with type 2 diabetes and demonstrated cardiovascular benefit in terms of reduction of a 3-point MACE composite endpoint as well as of hospitalization for heart failure. However, it has not been studied shortly after myocardial infarction yet. Given that the drug is not causing hypoglycemic events per se, hypoglycemia appears not to be a major issue in subjects without diabetes, that are studied in this trial as well. When

Protocol No: Version 2.17 Date: 17 October 2022

Empagliflozin is used together with sulfonylurea or insulin, hypoglycemia might occur and therefore participants will be instructed to reduce concomitant antihyperglycemic medication accordingly.

Fungal genital infections are the most common side effect of Empagliflozin and participants will be informed about this and instructed on prevention measures. Rarely, serious infections of the genitals and the area around the genitals have been reported. This infection, called necrotizing fasciitis of the perineum, is also referred to as Fournier's gangrene.

In people with type 2 diabetes mellitus, the risk for ketoacidosis is increased, in particular in situations such as insulin deficiency, alcohol abuse, exsiccosis or infections.

There will be no direct beneficial effect for all participants, however, those participants with known diabetes mellitus type 2 randomised to the Empagliflozin group will benefit from the glucose lowering effect of the drug.

Overall this trial aims to develop novel future strategies for heart failure prevention in subjects with acute myocardial infarction.

## 6. ADVERSE EVENTS (AE)

An AE is any untoward medical occurrence in a patient or clinical trial subject administered a medicinal product and which does not necessarily have a causal relationship with this treatment. An AE can therefore be any unfavourable and unintended sign (including an abnormal laboratory finding), symptom, including an exacerbation of a pre-existing condition, or disease temporally associated with the use of the trial device/procedure, whether or not considered related to the treatment.

All adverse events that occur during this study will be recorded on the adverse event case report forms.

#### 6.1 Adverse Event description

For the purposes of the study, AEs will be followed up according to local practice until the event has stabilised or resolved, or the Follow-up Visit, whichever is the sooner. SAEs will be recorded throughout the study.

#### 6.2 Severity of Adverse Events

Mild: Awareness of event(s) or sign(s) but easily tolerated

Moderate: Discomfort enough to cause some interference with usual activity

Severe: Incapacitating or causing inability to carry out usual activity

## 6.3 Causality of Adverse Events

Medical judgment should be used to determine the relationship, considering all relevant factors, including pattern of reaction, temporal relationship, de-challenge or re-challenge, confounding factors such as concomitant medication, concomitant diseases and relevant history. Assessment of causal relationship should be recorded in the case report forms.

Yes: There is a reasonable causal relationship between the investigational product administered and the AE.

No: There is no reasonable causal relationship between the investigational product administered and the AE.

Protocol No: Version 2.17

#### Date: 17 October 2022

#### 6.4 Abnormal Laboratory Test Results

All clinically significant abnormal laboratory test results besides Troponin T (Troponin I), creatinkinase, nt-proBNP occurring during the study will be recorded as adverse events.

## 6.5 Adverse events of Special Interest (AESIs)

The term AESI relates to any specific AE that has been identified at the project level as being of particular concern for prospective safety monitoring and safety assessment within this trial, e.g. the potential for AEs based on knowledge from other compounds in the same class. AESIs need to be reported to the Pharmacovigilance Department of Boehringer Ingelheim within the same timeframe that applies to SAEs.

Patients with AESIs need to be followed up appropriately, regardless of the origin of the laboratory data (e.g. central, local etc.). The Investigator should consider which, if any, concomitant therapies should not be taken during evaluation. Discontinued treatments can be reintroduced per Investigator discretion.

The following are considered as AESIs:

## 6.5.1 Hepatic injury

A hepatic injury is defined by the following alterations of hepatic laboratory parameters after randomisation:

- an elevation of AST and/or ALT ≥ 3 fold ULN combined with an elevation of total bilirubin ≥ 2 fold ULN measured in the same blood sample
- an isolated elevation of ALT and/or AST ≥ 5 fold ULN

These laboratory findings constitute a hepatic injury alert and the patients showing these abnormalities need to be followed up according to medical judgement.

In case of clinical symptoms of hepatic injury (icterus, unexplained encephalopathy, unexplained coagulopathy, right upper quadrant abdominal pain, etc.) without laboratory results (ALT, AST, total bilirubin) available, the Investigator should make sure these parameters are analysed, if necessary in an unscheduled blood test.

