#### 2.3 Safety objectives

- All-cause mortality
- Number of serious adverse events
- Number of hypoglycemic events
- Number of genital infections
- Number of ketoacidotic events
- Changes in liver function parameters (AST, ALT, GGT)
- Changes in renal function parameters (creatinine, eGFR)

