#### 5.3 Visit schedule

	Visit 1 (V1) Screening / Baseline	Visit 2 (V2) (week 6 ± 2)	Visit 3 (V3) (week 12 ± 2)	Visit 4 (V4) (Week 26 ± 2)	Visit 5 (V5) (4 weeks ±1w after V4)
Informed Consent	X				
Inclusion/exclusion criteria	X				
Randomisation	Х				
Demography, medical history	х				
Concomitant medication	Х	Х	Х	Х	
Vital signs	Х	х	Х	Х	
Height	Х				
Weight	Х	х	х	Х	
Physical examination	х	х		Х	
ECG	х				
Cardiac ultrasound	Х	Х		Х	
Biobank sampling	Х	Х		Х	
nt-proBNP (local)	Х	х	х	Х	
Blood sampling	Х	х	Х	Х	
Liver function parameters (AST, ALT, GGT)	Х	х	Х	Х	
Renal function parameters (creatinine, eGFR)	Х	х	Х	Х	
Adverse Events		Х	Х	Х	Х

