#### Protocol No: Version 2.17

#### Date: 17 October 2022

Fasting glucose	Х	Х	Х	Х
Myoglobin	X			
pH (arterial/venous)	Х			
Urine Albumin/Creatinine Ratio (ACR)	Х	Х		Х

Table 2 Summary of blood tests at each study visit

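### One of the two laboratory definitions of the hepatic-injury AESI needs total bilirubin, which no scheduled follow-up panel contains, so that definition is not systematically ascertained

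*Protocol*

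**What the plan says.** Protocol 6.5.1 covers laboratory changes after randomisation and gives two definitions of hepatic injury. The first pairs AST or ALT of at least 3 × ULN with an "elevation of total bilirubin ≥ 2 fold ULN measured in the same blood sample". The second is "an isolated elevation of ALT and/or AST ≥ 5 fold ULN". Either finding raises the alert on its own; symptoms are not part of either definition.

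The same section adds a rule for patients who do have symptoms. If they present "without laboratory results (ALT, AST, total bilirubin) available", then "the Investigator should make sure these parameters are analysed, if necessary in an unscheduled blood test". Protocol 6.5 requires follow-up of patients with AESIs "regardless of the origin of the laboratory data (e.g. central, local etc" and puts AESIs on the same reporting clock as serious adverse events.

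The scheduled tests are narrower:
- Table 1 (Protocol 5.3) has one liver row, "Liver function parameters (AST, ALT, GGT", marked at visits 1 to 4.
- Table 2 (Protocol 5.5.5), captioned "Table 2 Summary of blood tests at each study visit", has rows for the same three enzymes and none for bilirubin.
- The liver safety objective (Protocol 2.3) is "Changes in liver function parameters (AST, ALT, GGT".
- The SAP repeats the three enzymes in its safety objectives (2.1.3) and its assessment schedule (3.4).

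Total bilirubin is named in Protocol 6.5.1 and nowhere else in either document.

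**The concern.** A laboratory definition can be applied evenly only if every analyte in it is measured on a common schedule. Here the second analyte of the combined definition is not scheduled at all. Whether a patient is found to meet it depends on symptoms, or on a local laboratory having run bilirubin for another reason.

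Protocol 6.5 describes AESIs as events of particular concern for prospective monitoring. If the combined criterion is looked for only in some patients, a low or zero count says little, because most patients may never have had the result that decides it. What would be lost is the AESI classification and the accelerated report that follows from it.

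The renal AESI in 6.5.2 makes a useful contrast. Its single analyte, creatinine, is drawn at visits 1 to 4, and a laboratory value alone calls for a further unscheduled sample.

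**Working it through.** The plan gives no figure to reproduce. The check compares the analytes that the definitions need with the analytes that are scheduled.

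**Step 1. Visits that count.** The definition is restricted to changes after randomisation. Visit 1 is screening and baseline, and Protocol 5.4 lists its blood collection before randomisation. The scheduled draws that can show the event are therefore visits 2, 3 and 4.
- Upper bound, all 476 patients at every visit: 476 × 3 = 1,428 samples.
- With the 216 per group that Protocol 7.1 needs after dropout: 2 × 216 × 3 = 1,296 samples.

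**Step 2. Needed against scheduled.**

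| Definition in 6.5.1 | Analytes needed | Scheduled at visits 2–4 | Follow-up visits at which it can be assessed |
|---|---|---|---|
| Combined (3 × ULN with bilirubin 2 × ULN) | AST or ALT, plus total bilirubin | AST and ALT only | 0 of 3 |
| Isolated (5 × ULN) | AST or ALT | AST and ALT | 3 of 3 |

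**Step 3. A symptom-free patient at a scheduled follow-up visit.**

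| AST or ALT | Isolated definition | Combined definition |
|---|---|---|
| Below 3 × ULN | not met | not met, whatever the bilirubin |
| 3 to below 5 × ULN | not met | depends wholly on bilirubin, which is not measured |
| 5 × ULN or more | met | not needed: already an AESI |

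The gap is the middle row only.

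**Step 4. Does another rule supply the missing test?**
- The unscheduled test in 6.5.1 is triggered by clinical symptoms, so it does not reach this patient.
- The sentence in 6.5 on the origin of laboratory data governs follow-up of a patient who already has an AESI. It lets an outside result count but does not order one.
- Protocol 6.4 has clinically significant abnormal results recorded as adverse events. It applies to tests that were done and does not add one.

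**Step 5. Could a bilirubin row have been lost from Table 2?** In the text copy, Table 2 has a row of four marks without a label directly above the sodium, potassium and chloride label, which has no marks. These fit together as one split row. The haematology row also carries one mark too many, so Table 2 alone does not settle the matter. Table 1, the SAP schedule and both lists of safety objectives each name only AST, ALT and GGT, which makes a lost row unlikely.

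**The case against.** The strongest reply has five parts.

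**The definition can still be met.** A reader might infer that the combined criterion can never be satisfied in this trial and that only the 5 × ULN rule can operate. The documents do not support that. A symptomatic patient should have bilirubin analysed and, because it is not scheduled, the condition that results are unavailable will usually apply. Routine-care results count too. This part stands, and it confines the point to scheduled samples.

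**The patient is not invisible.** A reader might also infer that such a patient is never identified. AST and ALT are measured at every visit. A rise judged clinically significant is recordable as an adverse event under Protocol 6.4, and the paragraph on laboratory changes in 6.6 says much the same. This stands: what can be lost is the AESI label and its accelerated report.

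**No planned comparison changes.** The SAP safety section names tables for deaths and serious adverse events, including diabetic ketoacidosis, and no hepatic AESI table. In a double-blind trial, missed labelling should be similar in the two arms. This largely stands. It limits the consequence but does not make the criterion assessable, and similar under-ascertainment in both arms still leaves a low count uninformative.

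**Event-driven work-up is the protocol's pattern.** The ketoacidosis criteria in Table 3 use bicarbonate and urine ketones, which Table 2 does not list, and pH, which it lists at visit 1 only. The parallel is partial. Section 6.5.3 calls for investigation of a suspected event and says that not all criteria need apply. Section 6.5.1 sets fixed laboratory thresholds that raise an alert without symptoms.

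**It is late to change the schedule.** The synopsis gives last patient out as 03/MAY/2022 and database lock as 17/MAY/2022, while this protocol version is dated 17 October 2022. This stands, and it is why the fix has a reporting part.

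**Conclusion.** The mismatch is real and limited. Protocol 6.5.1 uses an analyte that no scheduled panel in the protocol or SAP contains, so the combined criterion can be assessed at 0 of the 3 scheduled follow-up visits, covering at most 1,428 samples. The exposed group is symptom-free patients with AST or ALT from 3 to below 5 × ULN, raised bilirubin, and no incidental bilirubin result. They can be missed as AESIs.

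The 1,428 is the number of scheduled samples in which the criterion cannot be assessed. It does not count missed events: neither document gives a rate from which those could be estimated. Counting all four draws (4 × 476 = 1,904) would wrongly include the baseline sample.

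The conclusion assumes that Table 2 is complete as read and that local laboratories do not add bilirubin as a matter of course. If some do, ascertainment is better at those sites but still not uniform. The primary analysis and the sample size are unaffected. The documents give no ground for inferring a difference between arms or a hidden liver signal.

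**What to change.** Reconcile Protocol 6.5.1 with Tables 1 and 2 and with the schedule in SAP 3.4, so that the analyte the definition uses is measured in the blood already drawn at visits 2 to 4. The definition itself need not change. The cost is protocol and SAP wording and one routine analyte per sample, with no extra visit or draw.

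Where samples have already been taken without bilirubin, which the synopsis dates suggest is the case here, the remedy is in the reporting:
- tabulate the combined and the isolated criterion separately, by arm;
- beside each, give the number of patients with a bilirubin result after randomisation, so that the denominator for the combined criterion is visible;
- state that the combined criterion was not systematically ascertained.

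This costs one table and one sentence. Stored biobank material would not fully close the gap, since Table 1 schedules no biobank sample at visit 3.

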#### 6.5.2 Decreased renal function

Decreased renal function is defined by a creatinine value showing a  $\geq$  2 fold increase from baseline and is above the ULN.

For the AESI "decreased renal function" the Investigator shall collect an unscheduled laboratory sample for creatinine as soon as possible and initiate follow-up laboratory tests of creatinine according to medical judgement.

## 6.5.3 Metabolic acidosis, ketoacidosis and diabetic ketoacidosis (DKA)

In case of metabolic acidosis, ketoacidosis and DKA further investigations should be done according to the medical judgment and the clinical course until a diagnosis is made and/or the patient is recovered.

DKA is defined by the diagnostic criteria in the table below, and as defined by the American Diabetes Association (ADA).

Investigators should note that not all criteria in the table below need to apply for the diagnosis of DKA, and clinical judgment should also be taken into consideration. Due to its mechanism of action, Empagliflozin may potentially

#### Protocol No: Version 2.17

#### Date: 17 October 2022

modify the clinical presentation of DKA which may occur at lower plasma glucose levels than stated in the table below.

	DKA		
	Mild	Moderate	Severe
Plasma glucose (mg/dL)	>250	>250	>250
Arterial pH	7.25-7.30	7.00-7.24	<7.00
Serum bicarbonate (mEq/L)	15-18	10 to <15	<10
Urine ketones*	Positive	Positive	Positive
Serum ketones*	Positive	Positive	Positive
Effective serum osmolality (mOsm/kg)**	Variable	Variable	Variable
Anion gap***	>10	>12	>12
Alteration in sensoria or mental obtundation	Alert	Alert/drowsy	Stupor/coma

Table 3 Diagnostic criteria for DKA

- \* Nitroprusside reaction method
- \*\* Calculation: 2[measured Na (mEq/L) + glucose (mg/dL)/18
- \*\*\* Calculation: (Na+) (Cl- + HCO3-) (mEq/L)

## 6.5.4 Events involving lower limb amputation

This definition includes amputation (i.e. resection of a limb through a bone), disarticulation (i.e. resection of a limb through a joint) and auto-amputations (i.e. spontaneous separation of non-viable portion of the lower limb).

Not included in this definition are debridement (removal of callus or dead tissue), procedures on a stump (like stump revision, drainage of an abscess, wound revision etc.) and other procedures (e.g., nail resection or removal) without a concomitant resection of a limb (amputation or disarticulation).

Each lower limb amputation, disarticulation, or auto-amputation should be reported separately. The SAE report should include the date of the procedure, the level of amputation or disarticulation, the medical condition(s) leading to the procedure and if the patient had some of the known risk factor(s) for lower limb amputation.

6.6 Serious Adverse Events (SAE)

An SAE is defined as any event that

- Results in death;
- Is immediately life-threatening\*;
- Requires hospitalisation or prolongation of existing inpatient's hospitalisation\*\*
- Results in persistent or significant disability or incapacity;
- Is a congenital abnormality or birth defect;
- \* "Life-threatening" in the definition of "serious" refers to an event in which the subject was at risk of death at the time of the event; it does not refer to an event which hypothetically might have caused death if it were more severe.
- \*\* "Hospitalisation" means any unexpected admission to a hospital department. It does not usually apply to scheduled admissions that were planned before study inclusion or visits to casualty (without admission).

Protocol No: Version 2.17 Date: 17 October 2022

Medical judgement should be exercised in deciding whether an adverse event/reaction is serious in other situations. Important adverse events/reactions that are not immediately life-threatening, or do not result in death or hospitalisation but may jeopardise a subject, or may require intervention to prevent one of the other outcomes listed in the definition above should also be considered serious.

Patients may be hospitalised for administrative or social reasons during the study (e.g. days on which infusion takes place, long distance from home to site,). These and other hospitalisations planned at the beginning of the study do not need to be reported as a SAE in case they have been reported at screening visit in the source data and have been performed as planned.

## Worsening of the underlying disease or other pre-existing conditions

Worsening of the underlying disease or of other pre-existing conditions will be recorded as an (S)AE in the (e)CRF.

## Changes in vital signs, ECG, physical examination, and laboratory test results

Changes in vital signs, ECG, physical examination and laboratory test results will be recorded as an (S)AE in the (e)CRF, if they are judged clinically relevant by the investigator.

#### 6.6.1 Reporting of SAEs

The Sponsor shall report (i.e., from signing the informed consent onwards through the trial defined follow-up period <please define>) all SAEs and non-serious AEs which are relevant for a reported SAE and Adverse Events of Special Interest (AESI) by fax or other secure method using BI IIS SAE form to the BI Unique Entry Point immediately (within twenty four (24) hours or next business day whichever is shorter).

BI Unique Entry Point:
Boehringer Ingelheim RCV GmbH & Co KG,
Pharmacovigilance Austria
[name], [name], Austria

[contact] [contact]

E-mail: PV local [contact]

For each adverse event, the investigator will provide the onset date, end date, intensity, treatment required, outcome, seriousness, and action taken with the investigational drug. The investigator will determine the expectedness of the investigational drug to the AEs as defined in the Listed Adverse Events section of the Boehringer Ingelheim's (BI's) Investigator Brochure for the Productor BI Drug Information e.g. Summary of Product Characteristics (SmPC) or Product Information (PI) for the authorised Study Drug provided by BI,

The investigator does not need to actively monitor patients for adverse events once the clinical trial has ended. However, if the investigator becomes aware of an SAE(s) that occurred after the patient has completed the clinical trial (including any protocol specified follow-up period), it should be reported to BI if investigator considers it as relevant to the BI study drug.

Protocol No: Version 2.17 Date: 17 October 2022

The sponsor will report the SAE to the ethics committee and the local authorities as well as Boehringer Ingelheim Pharmacovigilance in accordance with the aforementioned SAE reporting instructions.

A suspected unexpected serious adverse reaction (SUSAR) is designated as such according to Guideline 2001/20/EG. A serious adverse reaction is deemed unexpected when it is not listed in the corresponding basic document (Summary of Product Characteristics, IB, IMPD).

#### 7. STATISTICAL ANALYSES

#### 7.1 Sample size and power considerations

Previous data showed that nt-proBNP levels decrease by about 50% within 6 months after acute myocardial infarction. To detect a relative 40% larger reduction in nt-proBNP levels in the Empagliflozin group as compared to the placebo group with a power of 80% and an alpha-level of 0.05%, and assuming a correlation for nt-proBNP levels of 0.85, a sample size of 216 subjects in each group is necessary. To account for a dropout rate of about 10% each group will consist of 238 patients.

#### 7.2 Data analysis

Patient characteristics will be summarized. Summaries of continuous variables will be presented as means and standard deviations, if normally distributed, and as medians and inter-quartile ranges for skewed data, whilst categorical variables will be presented as frequencies and percentages. The analysis will be performed according to the intention to treat principle. All statistical tests will be two-tailed with a 5% significance level.

Analysis will be based on the intention to treat cohort, while a sensitivity analysis for the per-protocol group will be done in addition. A detailed statistical analysis plan including pre-specified subgroup analyses will be finalized ahead of database lock.

